2.3 Exploratory Objectives

To determine:

- Undetectable PSA at 11 months (cycle 11) (irrespective of testosterone level)
- Time to PSA progression defined as the time to PSA increase that is $\geq 25\%$ and $\geq 2\text{ng/mL}$ above the nadir, and which is confirmed by a second value > 3 weeks later
- Change in PSA doubling time at 24 months relative to PSA doubling time from the first dose of study drug (using the last 3 values from each time point)
- Comparison of Patient Reported Outcome (PRO) assessments of toxicity (PRO-CTCAE) to clinician reported toxicity assessments (CTCAE v.5.0)
- Changes in immune biomarkers with treatment. Peripheral blood mononuclear cells (PBMCs) will be collected that can later be analyzed for the immunomodulatory effects of the regimen by measuring for example, discrete T-cell populations. Archival tissue will also be analyzed for immune-related genes that may associate with response.

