7.2.2 Grading severity

All adverse events will be graded based on the NCI CTCAE version 5.0. A copy of the CTCAE Version 5.0 can be downloaded from the CTEP home page (<http://ctep.cancer.gov>). All appropriate treatment areas should have access to a copy of the CTCAE Version 5.0.

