10. STATISTICAL CONSIDERATIONS

10.1 Study Endpoints

10.1.1 *Primary endpoint*

Undetectable PSA with recovered testosterone (non-castrate defined as testosterone > 150ng/dL) at 24 months. Undetectable is defined as PSA < 0.05 ng/ml. For institutions where the lower limit of detectable is 0.10 ng/ml, then undetectable will be defined as PSA <0.10 ng/ml.

10.1.3 *Secondary endpoints*

- Undetectable PSA at 5 months (with the combination of durvalumab and olaparib, no ADT)
- Safety of the combination of durvalumab and olaparib will be determined by the summary of AEs

10.1.4 *Exploratory endpoints/correlative studies*

- Measurement of patient reported toxicities using PRO-CTCAE at screening, cycle 5, cycle 11, and EOT. Changes over time and comparison to clinician reported toxicities (CTCAE v5.0)
- Blood biomarkers at cycle 1, cycle 2, cycle 5, cycle 11, and end of treatment: PBMCs collected to assess immunomodulation, for example, changes in T -cell populations over time, multiplex cytokine analysis, tumor associated antigens; cfDNA will also be collected at cycle 1, cycle 5 and end of treatment for potential future use.
- Archival tissue for analysis of immune activating genes and PDL1 expression
- Undetectable PSA at 11 months (irrespective of testosterone level)
- PSA PFS
- Change in PSA doubling time relative to trial entry

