10.2 Sample Size Determination

The primary objective of the study is to determine the efficacy of the combination of olaparib with durvalumab in subjects with biochemically recurrent castration sensitive disease. The primary endpoint of the study is maintaining an undetectable PSA with recovered testosterone at 24 months and this event is defined as a success. Subjects that withdraw prior to the 24 month follow up time are deemed as failures for the primary endpoint. A single stage design that differentiates between population success rates of 0.15 and 0.35 will be used to assess treatment activity.⁶³

Thirty-two subjects will be accrued to this trial. If eight or more successes are observed, it is concluded that the therapy is sufficiently active to warrant further study. This design has power greater than 0.90 for a population success proportion of 0.35 using a one-sided test with size 0.10 for the population success rate 0.15.

In addition to the evaluation of the primary endpoint, the study will be monitored for unacceptable toxicity, which is defined as Grade 3 or greater immune related toxicity requiring steroids or \geq Grade 3 non-immune toxicity requiring trial discontinuation. The stopping rule for excessive toxicity and the corresponding power calculation is provided in the table below.

Toxicity	# of toxicities needed to stop the study	Toxicity rate in the population	Probability boundary is crossed
\geq Grade 3 immune related toxicity requiring steroids or \geq Grade 3 non-immune toxicity requiring trial discontinuation	4 in the first 8 subjects	0.15	0.11
	5 in the first 16 subjects 7 in the first 24 subjects 9 within 32 subjects	0.35	0.89

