10.5 Statistical Procedures and Analysis

Summary statistics include the number of observations, mean, standard deviation, median, minimum, and maximum values.

Statistical methods for the analyses

An exact binomial test will be used to evaluate the efficacy of the 24 months undetectable PSA endpoint. In addition, the proportion of subjects that attain an undetectable PSA at (1) 5 months, (2) 11 months, and (3) 24 months will be computed along with their attendant 95% confidence intervals. The probability of PSA progression over time will be estimated using the cumulative incidence function.

A paired t-test will be used to compare the PSA doubling time at 24 months to the PSA doubling time at study entry.

Kendall's tau with longitudinal data will be used to compare patient recorded toxicities to physician recorded toxicities over time.

The immunologic profile of patients over time will be described using nonparametric kernel smoothing.

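### Kendall's tau alone answers the exploratory patient-versus-clinician toxicity comparison only in part: it shows neither the direction nor the size of a difference

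*Combined protocol and SAP*

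**What the plan says.** Section 2.3 lists among the exploratory objectives: "Comparison of Patient Reported Outcome (PRO) assessments of toxicity (PRO-CTCAE) to clinician reported toxicity assessments (CTCAE v.5.0"). Section 10.1.4 repeats the comparison as an exploratory endpoint, adds change over time, and gives the schedule: "Measurement of patient reported toxicities using PRO-CTCAE at screening, cycle 5, cycle 11, and EOT".

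Section 10.5 assigns one method: "Kendall's tau with longitudinal data will be used to compare patient recorded toxicities to physician recorded toxicities over time". It does not say which longitudinal form of tau is meant, or whether it is computed per symptom. On the clinician side, Section 7.2.2 states: "All adverse events will be graded based on the NCI CTCAE version 5.0".

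Nothing else in the plan pairs the two sources. The general sentence in Section 10.5, "Summary statistics include the number of observations, mean, standard deviation, median, minimum, and maximum values", is not tied to a patient-minus-clinician difference. The adverse-event summaries in Section 10.4.1 have no patient-reported counterpart. No significance level, margin or threshold is set for this comparison.

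**The concern.** A comparison of two sources of toxicity data raises two questions. Do they order subjects similarly, and do they report the same amount? Tau addresses the first. It depends only on whether pairs of subjects are ordered the same way by both sources, so a strictly monotone shift in one source leaves it unchanged. It is also symmetric, so swapping patient and clinician gives the same value. Extending it to repeated visits deals with the data structure, but the result is still a measure of concordance.

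The risk is one of interpretation. A high tau could be reported as good concordance when one source records a symptom much less often than the other. The reader would have no figure from which to see that.

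**Working it through.** The plan gives no figure for this comparison, so there is none to reproduce. The check asks what tau returns when the difference between sources is known.

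**Inputs.** From the plan: 32 subjects (Section 10.2); up to four assessments per subject (Section 10.1.4). Assumed, because the documents give none: the grade distributions, a common 0 to 4 scale, and one visit per subject.

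**Formula.** tau-b = (C − D) / √[(n0 − Tp)(n0 − Tc)]. Here n0 = 32 × 31 / 2 = 496 pairs of subjects, C and D are the concordant and discordant pairs, and Tp and Tc are the pairs tied on patient and on clinician grade.

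**Step 1: a pure shift, no floor.** Patient grades 1/2/3/4 in 8/12/8/4 subjects.

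| Clinician grade | tau-b | Mean difference (clinician − patient) | Exact agreement |
|---|---|---|---|
| Equal to patient | 1.00 | 0 | 100% |
| Always one lower | 1.00 | −1.00 | 0% |
| Always one higher | 1.00 | +1.00 | 0% |

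This is an extreme case: nobody has grade 0, so no floor ties arise, and exact agreement has meaning only on a common scale.

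**Step 2: a floor at zero.** Patient grades 0/1/2/3/4 in 8/10/8/4/2 subjects; clinician one grade lower, but not below 0.
- C = 308, D = 0, Tp = 108, Tc = 188.
- tau-b = 308 / √(388 × 308) = 0.89, and 0.89 again with the sources swapped.
- Patients report the symptom in 24/32 (75%) and clinicians in 14/32 (44%). Clinicians miss 10 of 24, a gap of 10/32 = 31 percentage points.
- If clinicians instead record only the grade 1 symptoms as none and grade the rest correctly, tau-b is again 0.89, while exact agreement rises from 8/32 (25%) to 22/32 (69%). Two different error patterns give one tau.

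**Step 3: symptoms mostly absent or mild.** Same clinician rule; both error patterns again give the same tau-b.

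| Patient grades 0/1/2/3/4 | tau-b | Missed by clinician | Gap in detection |
|---|---|---|---|
| 8/10/8/4/2 | 0.89 | 10 of 24 | 10/32 = 31 points |
| 14/12/4/2/0 | 0.70 | 12 of 18 | 12/32 = 38 points |
| 16/12/3/1/0 | 0.61 | 12 of 16 | 12/32 = 38 points |
| 20/9/2/1/0 | 0.58 | 9 of 12 | 9/32 = 28 points |

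Ties do lower tau. But the lowest tau goes with the smallest gap, so the gap cannot be read off tau.

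**Step 4: with noise.** 1,000 simulated sets of 32 pairs. Patient grades 0 to 4 had probabilities 0.30, 0.30, 0.20, 0.13 and 0.07. The clinician grade was the patient grade plus the shift plus an error of −1, 0 or +1 (probabilities 0.2, 0.6, 0.2), limited to 0 to 4.

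| Clinician shift | Mean tau-b | Mean difference | Signed-rank test rejects at 0.05 |
|---|---|---|---|
| One lower | 0.77 | −0.64 | 100% |
| None | 0.82 | +0.05 | 7% |
| One higher | 0.80 | +0.91 | 100% |

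Tau was significant at 0.05 in every run of all three settings. A paired measure separates the settings; tau barely does.

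**Step 5: precision of the added measure.** In Step 2, 10 subjects are positive by patient only and none by clinician only. The difference is 10/32 = 0.31, with standard error √[(10 − 10²/32)/32²] = √(6.875/1024) = 0.082. The approximate 95% interval is 0.31 ± 0.16, or 0.15 to 0.47. That is wide but informative, and it widens as subjects leave before cycle 11.

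**The case against.** The strongest case on the other side has four parts.

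- **The aim.** A reader might infer that the method fails a stated goal of detecting clinician under-reporting, or leaves the comparison unanswered. The documents do not support that. Sections 2.3 and 10.1.4 ask for a comparison and name neither under-reporting nor agreement. Rank association over time is one legitimate part of a comparison.
- **The size.** A reader might infer that tau stays at or near 1.0 however much clinicians miss. It does not. When symptoms are mostly absent or mild, ties bring it down to 0.58 to 0.70 even without noise (Step 3).
- **The scales.** The Appendix F items are not visible in the text available. If the patient and clinician instruments use different scales, exact agreement on raw grades has little meaning and a rank measure is a sensible choice. This stands, and it is a reason to keep tau. It does not rule out comparing presence with absence, but it limits that to symptoms that can be mapped.
- **Baseline symptoms.** Ongoing conditions are recorded as medical history (Section 5.1.3), and adverse events are recorded from consent (Section 7.1.1). A long-standing symptom could be reported by the patient and correctly have no adverse-event entry. An uncritical any/none table, above all at screening, would then show false under-detection. This stands, and the fix must allow for it.

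The misreading of a high tau is also a prediction about readers, since no decision in the plan depends on the value. What survives all four is narrower: tau by itself gives neither the direction nor the size of a difference, and nothing else in the plan does.

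**Conclusion.** The point holds in this limited form. The plan's only method for the comparison covers association and leaves out level and detection. On the assumed distributions, detection gaps of 28 to 38 percentage points go with tau-b anywhere from 0.58 to 0.89, so tau is no guide to the gap. The value of 1.0 with no exact agreement is an extreme that presumes a common scale, and it should not be quoted as typical.

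The figures rest on assumed grades, a common scale and a single visit. The property itself rests on none of these: tau is symmetric and unchanged by a strictly monotone shift.

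This is a cheap improvement. The comparison is exploratory. The primary endpoint is PSA-based, and the secondary safety endpoint is a summary of adverse events that does not use this comparison, so neither conclusion changes.

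**What to change.** Keep Kendall's tau and state which longitudinal form is used and that it is computed per symptom. Then add the following to Section 10.5:

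1. Before analysis, list the PRO-CTCAE symptoms that map to a CTCAE term, with the mapping.
2. For each such symptom, give the paired any/none table (patient by clinician) at cycle 5, cycle 11 and end of treatment.
3. Count the clinician report as present if an adverse event, or a recorded ongoing baseline condition, covers the date of the PRO visit.
4. Report the difference in detection proportions with a bootstrap interval that resamples subjects and keeps all visits of a subject together.
5. Show the screening table descriptively only.

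The assessments are already scheduled, so no data, visits or patient burden are added. The cost is the symptom mapping, the alignment of adverse-event dates with PRO visits, and a few tables. With 32 subjects the intervals will be wide and some symptoms will have sparse cells, so the results should be presented as estimates, not tests.

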11. REGULATORY AND PROTECTION OF HUMAN SUBJECTS

11.1 Ethical Considerations

This study will be conducted in compliance with the protocol, GCP guidelines established by the International Conference on Harmonisation, as adopted by applicable laws and regulations, and the ethical standards set forth in the Declaration of Helsinki (available at: www.laakariliitto.fi/e/ethics/helsinki.html).

11.2 Protocol Amendments

Before starting the study, the protocol must be approved by each institution's IRB or Independent Ethics Committee (IEC). Amendments to the protocol may be made only with consent of the lead site/sponsor and PCCTC and are subject to IRB approval before instituting.

11.3 Written Informed Consent

Before obtaining consent, members of the study team will review the rationale for the treatment program with the subject. The discussion will review the alternatives available (including hormonal therapy, chemotherapy, or supportive care as appropriate), the potential benefits of this program, the risks and the probability of their occurrence, and the procedures to minimize these risks. Should an adverse event occur, the provisions available to ensure medical intervention will also be reviewed. Why the risks are reasonable in relation to the anticipated benefits, incentives, or costs that will or may be incurred as a result of participating in the study, as well as the efforts to maintain confidentiality, will also be discussed with the subject.

Subjects will be required to sign and date an informed consent form that meets the requirements of the Code of Federal Regulations and the IRB. The medical record will include a statement that written informed consent was obtained (and document the date that it was obtained) before the subject is enrolled in the study.

The consent form will include the following:

- the nature and objectives, potential toxicities, and benefits of the intended study
- the length of therapy and likely follow-up required
- alternatives to the proposed therapy (including available standard and investigational therapies)
- the name of the investigator(s) responsible for the protocol
- the right of the subject to accept or refuse treatment and to withdraw from participation in this study
- Text regarding the consortium and the coordinating center should be added to all institutional informed consent documents and sections in the research authorization/HIPAA forms (e.g., "Prostate Cancer Clinical Trial Consortium")

11.4 Protection of Privacy

Subjects will be informed of the extent to which their confidential health information generated from this study may be used for research purposes. After this discussion, they will be asked to sign a Notice of Privacy Practice research authorization/HIPAA form. The original signed documents will become part of the subject's medical records, and each subject will receive a copy of the signed documents. The use and disclosure of protected health information will be limited to the individuals described in the research authorization form. The research authorization form must be completed by the investigator and approved by the IRB.

11.5 Terminating or Modifying the Study

Adverse event and laboratory data from this trial will be assessed by the Sponsor Principal Investigator on an ongoing basis. SAEs will be reviewed as they are reported to the sponsor and PCCTC, and the Sponsor Principal Investigator will make an assessment regarding the safety of

continuing or modifying the study. This assessment will be shared with the investigators either in writing or as part of a teleconference. Should the assessment of either the lead site/sponsor or the principal investigator be that the study should be terminated, the study will be closed to further accrual. Subjects who are receiving an investigational agent(s) will be assessed individually by the investigator to see if it is in the subjects' best interest to continue, which might be the case for a subject that is responding to the intervention. Follow-up safety assessments will be performed for all subjects who are terminated from the study prematurely.

APPENDIX A: PERFORMANCE STATUS CRITERIA

ECOG Performance Status Scale		Karnofsky Performance Scale	
Grade	Description	%	Description
0	Normal activity. Fully active, able to continue all predisease performance without restriction.	100	Normal, no complaints, no evidence of disease
		90	Able to carry on normal activity, minor signs or symptoms of disease
1	Symptoms, but ambulatory. Restricted in physically strenuous activity but ambulatory and able to carry out work of a light or sedentary nature (e.g., light housework, office work).	80	Normal activity with effort, some signs or symptoms of disease
		70	Cares for self, unable to carry on normal activity or to do active work
2	In bed < 50% of the time. Ambulatory and capable of all self-care but unable to carry out any work activities. Up and about more than 50% of waking hours.	60	Requires occasional assistance but is able to care for most needs
		50	Requires considerable assistance and frequent medical care
3	In bed > 50% of the time. Capable of only limited self-care, confined to bed or chair > 50% of waking hours.	40	Disabled, requires special care and assistance
		30	Severely disabled, hospitalization indicated. Death not imminent.
4	100% bedridden. Completely disabled, cannot carry on any self-care, totally confined to bed or chair.	20	Very sick, hospitalization indicated. Death not imminent.
		10	Moribund, fatal processes progressing rapidly
5	Dead	0	Dead

Olaparib + Durvalumab
Memorial Sloan Kettering Cancer Center

c17-192

APPENDIX B: STUDY CALENDAR

(A cycle = 28 days; a month = 28 days)

	Screening		Treatment/Intervention Period									End of Treatment (EOT) within 30 days of last dose	Follow Up ^s	
			Cycle 1		Cycle 2		Cycle 3	Cycle 4	Cycle 5	Cycle 6	Cycle 7- Cycle 24			
	Day -42 to Day -1	Day -14 to Day -1	Day 1 (± 3 d)	Day 15, (± 3 d)	Day 1 (± 3 d)	Day 15 (± 3 d)	Day 1 (± 3 d)	(± 7 d)						
Informed consent and research authorization/ HIPAA form ^a	X													
Demographics, medical history, histologic confirmation	X													
Physical examination, Vitals (Blood Pressure, Pulse, Temperature), weight ^b	X		X	X	X	X	X	X	X	X	X	X	X	
Height	X													
12-lead EKG	X													

Olaparib + Durvalumab
Memorial Sloan Kettering Cancer Center

c17-192

	Screening		Treatment/Intervention Period								End of Treatment (EOT) within 30 days of last dose	Follow Up ^s
			Cycle 1		Cycle 2		Cycle 3	Cycle 4	Cycle 5	Cycle 6		
	Day -42 to Day -1	Day -14 to Day -1	Day 1 (± 3 d)	Day 15, (± 3 d)	Day 1 (± 3 d)	Day 15 (± 3 d)	Day 1 (± 3 d)	(± 7 d)				
Performance status	X		X	X	X	X	X	X	X	X	X	X
Concomitant medications	X		X	X	X	X	X	X	X	X	X	X
Adverse Events	X		X	X	X	X	X	X	X	X	X	X
Radiologic evaluations and measurements ^c	X		For non-metastatic, rising PSA subjects, radiologic tests are performed at Cycle 5 (+/- 2 week), Cycle 24 (+/- 2 week) or at EOT (+/- 2 week) if discontinued sooner.								X ^d	
CBC w/ diff plts ^e		X	X	X	X	X	X	X	X	X	X	X
Comprehensive Metabolic Panel ^f		X	X	X	X	X	X	X	X	X	X	X
Coagulation Tests ^g		X										
PSA ^h		X	X		X		X	X	X	X	X	X
TFTs ⁱ		X			X			X		X	X	X
Testosterone ^j		X								X	X	
Hepatitis Panel		X										
HIV		X										
Urinalysis ^k		X										

Olaparib + Durvalumab
Memorial Sloan Kettering Cancer Center

c17-192

	Screening		Treatment/Intervention Period								End of Treatment (EOT) within 30 days of last dose	Follow Up ^s
			Cycle 1		Cycle 2		Cycle 3	Cycle 4	Cycle 5	Cycle 6		
	Day -42 to Day -1	Day -14 to Day -1	Day 1 (± 3 d)	Day 15, (± 3 d)	Day 1 (± 3 d)	Day 15 (± 3 d)	Day 1 (± 3 d)	(± 7 d)				
PBMC ^t		X		X					X		X	X
PRO-CTCAE ^m	X								X		X	X
cfDNA ⁿ		X							X			X
PDL-1 Expression (archived tissue) ^o	X											
Tissue Sequencing ^p	X											
Normal Sample ^q	X											
Olaparib Administration ^r								X				
Durvalumab Administration ^r								X				
ADT Administration ^r								X				

- a. Informed consent and radiologic assessments should be obtained within 42 days.
- b. Refer to section 6.1 for monitoring of vital signs and observation period.

Olaparib + Durvalumab
Memorial Sloan Kettering Cancer Center

c17-192

- c. Radiographic evaluations will include CT CAP with contrast or MRI with contrast of the abdomen and pelvis, and CT chest without contrast. Radionuclide bone scan will be performed. All disease sites must be assessed using the same methodology as performed at baseline. At the discretion of the investigator, additional radiological evaluations may be performed at an unscheduled time point.
- d. If radiographic evaluations were completed within 30 days of EOT, they do not need to be repeated.
- e. CBC w/diff, platelets will be monitored biweekly during Cycle 1 and 2, and monthly from Cycle 3-Cycle 24 (see section 5.1.9 for additional information regarding laboratory tests)
- f. CMP will be monitored biweekly during Cycle 1 and 2, and monthly from Cycle 3-Cycle 24 (see section 5.1.9 for additional information regarding laboratory tests)
- g. APTT and INR. See section 5.1.9 for more information on coagulation tests.
- h. PSA will be collected monthly during each cycle.
- i. Thyroid function tests (TFTs), including TSH, free T4, and free T3 will be monitored every other cycle (beginning with Cycle 2, Cycle 4, Cycle 6, etc.)
- j. Testosterone will be monitored at Screening, Cycle 6, Cycle 11 and every other month from Cycle 12-Cycle 24
- k. Urinalysis: to be collected at screening. If clinically indicated, urinalysis should be performed while on treatment. See section 5.1.9 for additional information.
- l. Peripheral Blood Mononuclear Cells (PBMCs) will be drawn C1D1 before treatment, Cycle 2, Cycle 5, Cycle 11, and EOT.
- m. QoL Assessment (PRO-CTCAE) compared from screening, Cycle 5, Cycle 11, and EOT.
- n. Non-immune blood biomarkers: cfDNA from C1D1 before treatment, Cycle 5, and EOT.
- o. Tissue biomarkers: PDL1 expression at screening.
- p. Tissue sequencing does not need to be repeated if performed prior to consent and subject has a confirmed DDR mutation. If DDR mutation status is unknown or sequencing was not previously performed, archival tissue as well as a matched normal sample must be sent for Next Generation Sequencing. If available, additional archival tissue from all subjects should be sent and banked for future analysis of immune markers.
- q. A blood or saliva sample will be collected during screening as matched normal for sequencing for patients completing prospective Next Generation Sequencing using assays that require a matched normal sample.
- r. Subjects will be treated concurrently with olaparib + durvalumab continuously for 24 months. Durvalumab will be administered on Day 1 of each cycle (± 3). After the first 4 months, if a subject fails to achieve an undetectable PSA [PSA of <0.05 (or PSA <0.10 for institutions where this is the lower limit of detection) with the combination of olaparib and durvalumab, ADT will be added for 6 months (starting at Cycle 5) while continuing treatment with olaparib and durvalumab (see section 6.3 for additional details regarding ADT). For subjects who have an undetectable PSA after the first 4 months of treatment, they will continue on the combination of olaparib + durvalumab continuously for 24 months (without ADT). As long as it is believed that subjects are clinically benefiting, they will remain on treatment for up to 24 months with olaparib and durvalumab. For example, a subject with a PSA reduction that does not achieve an undetectable PSA would be allowed to remain on study for the duration of the trial. Subjects who meet progression criteria while on active therapy would come off of trial.
- s. Subjects who have an undetectable PSA after completion of protocol therapy will be followed every 12 weeks. PSA, CMP, CBC, and TFTs should be performed. A physical exam will be performed. Subjects who respond and later progress in the first year following the 24 month treatment phase will be allowed to re-induce with the combination and will restart their calendar with C1D1 if they continue to meet all clinical eligibility criteria are met. PCCTC must review the confirmation of eligibility prior to re-inducing treatment.

APPENDIX C. ACTIONS REQUIRED IN CASES OF COMBINED INCREASE OF AMINOTRANSFERASE AND TOTAL BILIRUBIN – HY'S LAW

Introduction

This Appendix describes the process to be followed in order to identify and appropriately report cases of Hy's Law. It is not intended to be a comprehensive guide to the management of elevated liver biochemistries. Specific guidance on the managing liver abnormalities can be found in Appendix H and Appendix I of the protocol.

During the course of the study the Investigator will remain vigilant for increases in liver biochemistry. The investigator is responsible for determining whether a subject meets potential Hy's Law (PHL) criteria at any point during the study.

The Investigator participates, in review and assessment of cases meeting PHL criteria to agree whether Hy's Law (HL) criteria are met. HL criteria are met if there is no alternative explanation for the elevations in liver biochemistry other than Drug Induced Liver Injury (DILI) caused by the Investigational Medicinal Product (IMP).

The Investigator is responsible for recording data pertaining to PHL/HL cases and for reporting Adverse Events (AE) and Serious Adverse Events (SAE) according to the outcome of the review and assessment in line with standard safety reporting processes.

Definitions

Potential Hy's Law (PHL)

Aspartate Aminotransferase (AST) or Alanine Aminotransferase (ALT) $\geq 3 \times$ Upper Limit of Normal (ULN) **together with** Total Bilirubin (TBL) $\geq 2 \times$ ULN at any point during the study following the start of study medication irrespective of an increase in Alkaline Phosphatase (ALP).

Hy's Law (HL)

AST or ALT $\geq 3 \times$ ULN **together with** TBL $\geq 2 \times$ ULN, where no other reason, other than the IMP, can be found to explain the combination of increases, e.g., elevated ALP indicating cholestasis, viral hepatitis, another drug.

For PHL and HL the elevation in transaminases must precede or be coincident with (i.e. on the same day) the elevation in TBL, but there is no specified timeframe within which the elevations in transaminases and TBL must occur.

Identification of Potential Hy's Law Cases

In order to identify cases of PHL it is important to perform a comprehensive review of laboratory data for any subject who meets any of the following identification criteria in isolation or in combination:

- ALT $\geq 3 \times$ ULN
- AST $\geq 3 \times$ ULN

- TBL \geq 2xULN

The Investigator should without delay review each new laboratory report and if the identification criteria are met will:

- Notify the PCCTC. The PCCTC will notify AstraZeneca when appropriate.
- Determine whether the subject meets PHL criteria (see Definitions within this Appendix for definition) by reviewing laboratory reports from all previous visits
- Promptly enter the laboratory data into the laboratory CRF

Follow-up

Potential Hy's Law Criteria not met

- Perform follow-up on subsequent laboratory results according to the guidance provided in the protocol.

Potential Hy's Law Criteria met

- Notify the PCCTC. The PCCTC will notify AstraZeneca when appropriate.

The Sponsor Principal Investigator contacts the Investigator, to provide guidance, discuss and agree an approach for the study subjects' follow-up and the continuous review of data. Subsequent to this contact the Investigator will:

- Monitor the subject until liver biochemistry parameters and appropriate clinical symptoms and signs return to normal or baseline levels, or as long as medically indicated
- Investigate the etiology of the event and perform diagnostic investigations as discussed with the Sponsor Principal Investigator.
- Enter data into the CRFs as information becomes available
- If at any time (in consultation with the Sponsor Principal Investigator) the PHL case meets serious criteria, report it as an SAE using standard reporting procedures

Review and Assessment of Potential Hy's Law Cases

The instructions in this Section should be followed for all cases where PHL criteria are met.

No later than 3 weeks after the biochemistry abnormality was initially detected, the Sponsor Principal Investigator contacts the Investigator in order to review available data and agree on whether there is an alternative explanation for meeting PHL criteria other than DILI caused by the IMP. The Lead Principal Investigator, PCCTC and AstraZeneca may also be involved in this review together with other subject matter experts as appropriate.

According to the outcome of the review and assessment, the Investigator will follow the instructions below.

If there is an agreed alternative explanation for the ALT or AST and TBL elevations, a determination of whether the alternative explanation is an AE will be made and subsequently whether the AE meets the criteria for a SAE:

- If the alternative explanation is **not** an AE, record the alternative explanation on the appropriate CRF
- If the alternative explanation is an AE/SAE, record the AE /SAE in the CRF accordingly

If it is agreed that there is **no** explanation that would explain the ALT or AST and TBL elevations other than the IMP:

- Report an SAE (report term 'Hy's Law').
 - The 'Medically Important' serious criterion should be used if no other serious criteria apply
 - As there is no alternative explanation for the HL case, a causality assessment of 'related' should be assigned.

If, there is an unavoidable delay, of over 3 weeks, in obtaining the information necessary to assess whether or not the case meets the criteria for HL, then it is assumed that there is no alternative explanation until such time as an informed decision can be made:

- Report an SAE (report term 'Potential Hy's Law') applying serious criteria and causality assessment as per above
- Continue follow-up and review according to agreed plan. Once the necessary supplementary information is obtained, repeat the review and assessment to determine whether HL criteria are met. Update the SAE report according to the outcome of the review

References

FDA Guidance for Industry (issued July 2009) 'Drug-induced liver injury: Premarketing clinical evaluation':
<http://www.fda.gov/downloads/Drugs/GuidanceComplianceRegulatoryInformation/Guidances/UCM174090.pdf>

